6.2.7 Study Day 28 (+/- 3 Days)

6.2.7.1 Clinical Data on Day 28

- Review symptoms and functional assessment (See Section 7.3.1)
- If Day 14 was a telephone visit contact – the diary cards for Day 7 – 14 are collected, and verified against the data obtained by telephone by the study staff.
- Assessment for presence of complications (See Section 7.3.2)
- If discharged – complete discharge assessment. If still hospitalized – assess if medically able to be discharged from hospital.
- Vital signs, including SaO₂ (See section 7.3.3)
- Review of concomitant medications
- Symptom targeted physical exam (for safety assessment, see Section 7.1.2)
- Assessment for AEs

6.2.7.2 Clinical Laboratory Tests on Day 28

The following laboratory test will be performed:

- CBC with differential white cell count (to include neutrophil, lymphocyte, and eosinophil percentages), hemoglobin, hematocrit, and platelets
- Blood chemistries (creatinine, ALT/GPT, AST/GOT, total bilirubin, LDH, CRP)

If these labs were performed for clinical care on this study day (or within the window), these labs do not need to be repeated and can be obtained from the clinical record.

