7.3 Efficacy Evaluations

7.3.1 Diary Card for Fever, Symptoms, and Functional Assessment

Subjects will maintain a diary card, and will be asked to make a daily entry in the evening. On Day 0, subjects will be instructed on the diary card and the initial (baseline) assessment will be

completed by the subject and collected. The subject will make daily entries through Day 14. The subject completes the final diary card at the time of the final visit on Day 28 to represent end of study functional assessment and symptoms.

Completion of subsequent diary cards should be done by the subject if possible. For children unable to complete the card, it may be completed by a parent or close relative (and documented accordingly). For those subjects too ill to complete the diary card, it may be completed by the study team or treating team (physicians or nurses) and this will be documented accordingly.

At each subsequent study visit, the diary card for the day(s) since the last visit will be collected. This diary will contain the information listed below (Section 7.3.1.1 – 7.3.1.3).

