### Secondary Endpoints:

#### Clinical Endpoints:

- Hospitalization on Study Days 3, 7, 14, and 28
- Date and time of hospital discharge
- Date of death, if applicable
- Clinical symptoms (measured daily through Study Day 14 and then again on Study Day 28)
- Temperature (measured daily through Study Day 14 and then again on Study Day 28)
- Oxygen use
- Date of admission to ICU and discharge from ICU, if applicable
- Date of intubation/extubation, if applicable
- Presence of complications during study (pneumonia, respiratory failure requiring mechanical ventilation, ARDS, sepsis, or bronchiolitis)
- Global assessment (measured daily through Study Day 14 and then again on Study Day 28) (defined in Section 7.3.1.3)
- Antibiotic/antiviral use during hospitalization (number and duration)
- Re-hospitalization within 28 days
- Use of systemic corticosteroids

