## 12. Secondary Endpoint (ITT and ITT age subgroups)

For secondary endpoints that test proportion:

- Deaths are always counted as worst case (i.e. deaths are counted as being hospitalized through Day 28).
- Missing data is analyzed in two ways:
  - Missing data is excluded after date of last follow-up. i.e. any analysis after the date of last follow up will exclude the missing subject from the denominator. This represents the “best case” for the missing data.
  - Missing data is assigned the worst case. i.e. for hospitalization, this missing data would be assumed to be hospitalized through Day 28. This represents the “worst case” scenario for the missing data.

For secondary endpoints that are time to events, the Fay-Shaw method accounts for deaths and missing data. In cases where the Fay-Shaw method is not appropriate, the Log-Rank p-value will be reported.

- Percent hospitalized at Study Day 3, 7, 14 and 28 [14.2.3.2.x]
  - Table N (%) hospitalized at Study Day 3, 7, 14 and 28 and test of proportions
  - Figure of proportions at each time point
- Duration of clinical symptoms [14.2.4.1.x]  
Subjects with 0-1 on all symptoms on Day 0 are considered to have a time of 0 hours.
  - Table: time (in hours) from symptom onset to symptom free (symptom free is 0-1 on all symptoms that last at least 2 days), noting min, 25%tile, 50%tile, 75%tile
    - P-value obtained using Shaw-Fay method (here only treat deaths as worst rank and missing as censored)
  - Figure using Kaplan-Meier plot.
- Duration of fever- defined as temperature  $\geq 38.0$  C [14.2.4.2.x]
  - Table: v with min, 25%tile, 50%tile, 75%tile, max.
    - P-value obtained using Shaw-Fay method (here only treat deaths as worst rank and missing as censored)

- Figure using Kaplan-Meier plot.
- Use of supplemental oxygen (or increase greater than baseline oxygen requirement) [14.2.5.1.x]
  - Resolution is defined as off oxygen. Subjects without stop date will be censored at 28 days. A time of 00:00 will be imputed for subjects with a stop date but missing stop time.
  - Table N (%) of use of oxygen (Y/N) at any point during the study, and at each time point
    - P-value obtained using test of proportions
  - Figure of proportions at each time point
  - Table duration of oxygenation: defined as time of oxygen first administered, to time off oxygen (in hours) noting min, 25%tile, 50%tile, 75%tile, max [14.2.5.2.x]
    - Table includes all subjects – where subjects not requiring oxygen have 0 hours.

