- Table duration of mechanical ventilation: defined as time subject placed on mechanical ventilation, to time extubated (removed from mechanical ventilation) noting min, 25%tile, 50%tile, 75%tile, max [14.2.7.3.x]
  - Table is restricted to those requiring mechanical ventilation at any point during the study.
  - P-value obtained using Shaw-Fay method (here only treat deaths as worst rank and missing as censored)
- Figure using Kaplan-Meier plot
  - Figure includes all subjects – where subjects not requiring mechanical ventilation have 0 hours.
  - Figure is repeated, but restricted to those requiring mechanical ventilation at any point during the study
- Proportion of subjects who develop complications including pneumonia, acute respiratory distress syndrome (ARDS), sepsis, or bronchiolitis at Day 3, 7, 14 and 28
  - Table for any complication: restricted to those subjects without any at baseline [14.2.8.1.x]
  - Figure of proportions at each time point
  - Table for each complication: restricted to those subjects without that complication at baseline [14.2.8.2.x]
    - Pneumonia
    - Respiratory failure requiring mechanical ventilation
    - ARDS
    - Sepsis
    - Bronchiolitis
  - Figure of proportions at each time point
- Global assessment [14.2.9.x]
  - Table duration (days) from enrollment until stating the first affirmative to global assessment questions
    - P-value obtained using Shaw-Fay method (here only treat deaths as worst rank and missing as censored)
  - Figure using Kaplan-Meier plot (time until stating the first affirmative).
  - There are two global assessment questions for adults and two global assessment questions for children. Each of these four questions will be analyzed separately.
- Antibiotic/antiviral use during hospitalization [14.2.10]

- Table N (%) of subjects with an antibiotic starting on or after Day 3
  - P-value obtained using test of proportions
- Systemic steroids use during hospitalization [14.2.10]
  - Table N (%) of subjects with systemic steroids starting after Day 3
    - P-value obtained using test of proportions
- Re-hospitalization within 28 days [14.2.10]
  - Table N (%) of subjects with rehospitalization within 28 days
    - P-value obtained using test of proportions
  - Listing of rehospitalizations: Randomized arm, days from randomization to re-hospitalization, subject ID, site, age, (sort by randomized arm, day from randomization)

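### SAP section 12 runs recovery times for symptoms and global assessment past the last daily diary entry (Day 14), so results beyond that day reflect the visit schedule

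*SAP*

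**What the plan says.** Protocol 7.3.1 sets the diary schedule: "The subject will make daily entries through Day 14", after which the subject "completes the final diary card at the time of the final visit on Day 28". The SAP's list of clinical endpoints repeats this for both outcomes at issue: "Clinical symptoms (measured daily through Study Day 14 and then again on Study Day 28" and "Global assessment (measured daily through Study Day 14 and then again on Study Day 28". Protocol 6.2.7 gives the last visit a window of plus or minus 3 days. It asks for a review of symptoms and function at that visit, and does not ask the patient to recall a recovery date.

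SAP section 12 then defines two recovery times on these data.

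- **Symptoms:** time from symptom onset until symptom-free, where "symptom free is 0-1 on all symptoms that last at least 2 days".
- **Global assessment:** "Table duration (days) from enrollment until stating the first affirmative to global assessment questions". No minimum duration is required. This is the only SAP analysis that can serve the secondary objective on resuming normal activity.

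Both get a Kaplan-Meier plot and a Shaw-Fay p-value, with deaths ranked worst and missing data censored. Neither has a stated horizon, a censoring day, or a rule for a patient who is unresolved on Day 14 and well at Day 28. For oxygen use, by contrast, the same section does name a censoring day.

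**The concern.** Recovery between Day 14 and the Day 28 visit cannot be observed on the day it happens. Days 15 to 27 are not missing data, because no entry was ever planned, so the instruction to censor missing data does not clearly apply.

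Followed as written, the two definitions treat the same patient in opposite ways: an event at about Day 28 for global assessment, a non-event for symptoms. The global curve will show a step at the final visit that marks when patients were asked. The symptom curve cannot fall after the daily entries end, even if Day 28 cards show that patients are well. If unresolved patients are carried to Day 28 before censoring, the flat stretch would read as if nobody had recovered.

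At stake are the Kaplan-Meier tails, any percentile lying beyond Day 14, and an analyst's choice that would otherwise be made after the data are in.

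**Working it through.** The plan states no figure on this point, so there is none to reproduce. The check applies the two event rules to the planned entry days.

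**Inputs.** Entries on Days 0 to 14 and at the Day 28 visit (Protocol 7.3.1); visit window Day 25 to 31 (Protocol 6.2.7); event rules from SAP section 12. The SAP gives no algorithm for the two-day rule, so three readings are shown: (a) two consecutive calendar days with entries; (b) two consecutive available entries; (c) a single last entry is accepted.

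| True first day of lasting recovery | Global: recorded day | Symptoms (a) | Symptoms (b) | Symptoms (c) |
|---|---|---|---|---|
| 11 to 13 | same day | same day | same day | same day |
| 14 | 14 | no event | 14 | 14 |
| 15 to 27 | Day 28 visit | no event | no event | 28 |
| 28 | Day 28 visit | no event | no event | 28 |

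For Days 15 to 27, readings (a) and (b) agree that there is no event. Reading (c) gives one only by dropping the two-day requirement.

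**Size of the dating error, global assessment.**
- Nominal schedule: 28 − 27 = 1 day to 28 − 15 = 13 days. If recoveries are spread evenly over the 13 days (assumption), the mean is (1 + 2 + … + 13)/13 = 91/13 = 7.0 days.
- With the window: a Day 25 visit leaves 25 − 15 = 10 days without entries, and a Day 31 visit leaves 31 − 15 = 16. The largest error is 16 days.

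**How many patients.** The documents give no share recovering in the gap. If it were 5%, 10%, 20% or 30% of 290 (assumption), about 14, 29, 58 or 87 patients would be affected.

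A rough indication comes from the placebo log-normal model in Protocol 9.2 (mean 1.83 and SD 0.66 on the log scale):
- Stay beyond 14 days: (ln 14 − 1.83)/0.66 = (2.639 − 1.83)/0.66 = 1.23, upper tail about 11%.
- Allowing for up to 60 hours (2.5 days) in hospital before enrollment (Protocol 4.4): (ln 16.5 − 1.83)/0.66 = (2.803 − 1.83)/0.66 = 1.47, upper tail about 7%.

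If inpatients do not yet report functioning as before (assumption), some 7% to 11% would be unresolved on Day 14 from this source alone. This is the share still unresolved, not the share recovering by Day 28.

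**Effect on the global assessment rank test.** Patients first answering yes at the Day 28 visit still rank after those who recovered on Days 0 to 14 and ahead of survivors not recovered. Only the order within the gap is lost. If a share q of each arm of 145 falls in the gap, the between-arm pairs affected are (145q)²/145² = q²: 0.25%, 1%, 4% and 9% for the four shares above.

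**The case against.** The best defence is that little is lost. The p-values are rank-based, and a Day 28 yes is correctly placed relative to every Day 0 to 14 recovery and every unrecovered survivor. Both blinded arms follow the same schedule. Requiring a two-day run for one endpoint and a first yes for another is a choice of definition, not in itself an inconsistency. All of this stands. It protects the rank test, but not the Kaplan-Meier tails or late percentiles that the SAP also reports.

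Several stronger readings are tempting, and the documents do not support them.

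- **A recovery on Day 14 can never count.** This holds only under reading (a). Under (b), scores of 0 to 1 on Day 14 and at Day 28 give an event on Day 14. The SAP leaves this open.
- **The 75th percentile will be exactly 28 days once more than a quarter of an arm is unresolved on Day 14.** The recorded day can be 25 to 31, and the percentile may not be reached at all. With 60% unresolved and 31% of the arm answering yes at Day 28, events total 40% + 31% = 71%.
- **Cards for Days 13 and 14 are lost after an in-person visit on Day 12.** Protocol 7.3.1 has each later visit collect the cards since the previous one, and that includes Day 28.
- **Fever duration fails in the same way.** The SAP gives fever neither the two-day rule nor the first-yes rule, and no fault is shown for it here.

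**Conclusion.** The point holds for two secondary endpoints, duration of symptoms and global assessment. As written, a first recovery on Days 15 to 27 is dated 1 to 13 days late for global assessment on the nominal schedule, and up to 16 days late with the visit window. For symptoms it is no event under the literal two-day rule. Curves and percentiles beyond Day 14 then describe the schedule rather than the patients.

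A reader might infer that these endpoints cannot be interpreted or that one arm is favoured. Neither follows: results up to Day 14 are sound, the permutation p-values remain valid though coarser, and the gap is the same in both arms. The primary endpoint rests on the date and hour of discharge and is unaffected.

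The dating error follows from the schedule alone. The number of patients affected is not known from the documents and rests on the assumptions shown.

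**What to change.** Amend SAP section 12 before unblinding, for symptoms and global assessment only:

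1. End the Kaplan-Meier curves and percentiles at the last daily diary entry, at most Study Day 14. Censor unresolved survivors there and keep deaths at worst rank.
2. Report unreached percentiles as >14 days. The symptom clock starts at onset rather than enrollment, so for that endpoint label them as not reached by Study Day 14.
3. Report Day 28 separately, as the proportion symptom-free and the proportion answering yes to each global question.
4. In the global assessment rank test, a first yes at the Day 28 visit may stay ranked after all Day 0 to 14 recoveries and ahead of survivors still not recovered. Treating these patients as tied stops the visit date from ordering them.
5. State whether a first symptom-free entry on Day 14 counts under the two-day rule.

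This is SAP wording only, with no new data and no change to visit windows or card collection. The cost is that no recovery time is estimated beyond Day 14; the Day 28 proportions carry the late information instead.

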9.1 General Considerations

This is a double-blind, randomized, placebo, controlled trial in patients with hospitalized influenza-like-illness to evaluate the efficacy of NTZ compared to placebo on the time to hospital discharge. The primary analysis will use the Shaw-Fay formulation of the 2 sample Mann-Whitney-Wilcoxon rank-sum statistic. The primary endpoint will be time to hospital discharge, censored at 28 days. Patients who withdraw consent will be counted as being censored at the time of withdrawal. Patients who die by Day 28 will receive the worst ranks, (i.e., worse than any patients who remain hospitalized). Furthermore, patients who die earlier will receive worse ranks than those who die later. Patients who withdraw consent prior to day 28 are thus censored for death and discharge at the time of withdrawal. Such censoring is addressed by the method of Shaw and Fay (2013). A permutation method will be used to determine statistical significance. The primary analysis will follow the intent-to-treat principle where all randomized patients will be used in the analysis. The primary analysis will use a two-sided alpha level of .05.

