## 11. Primary Endpoint (ITT, ITT age subgroups, ITT pediatric formulation subgroups, ITT virology subgroups)

Table to show the completeness of the primary endpoint should include number (%) with [14.2.2]:

- Complete data (Day of hospitalization and discharge or death)
- Incomplete data (missing day of hospitalization or discharge/death)

The following table and figure provide descriptive statistics of the primary endpoint. The table and figures should impute values of 28 days for patients who died and should censor patients with missing discharge date at the time of last follow up.

- Figure: Kaplan-Meier plot of time to hospital discharge/death (only ITT and ITT age subgroups)
- Table: with the following estimates from the Kaplan-Meier curves- 25th, 50th and 75th percentile along with min and max values in hours [14.2.3.1.x]

- The between group difference in median time to discharge will be used to estimate the treatment effect and will be reported along with a 95% two-sided confidence interval.
- Additionally, data from median, min, max converted to “days, hours”
- The p-value for the 2 group comparison of the primary endpoint analysis will be performed using the Shaw-Fay method as described in appendix 1.
- Sensitivity analyzes to exam effect of missing death or discharge data. (only ITT and ITT age subgroups)
  - Figure with Kaplan-Meier curves and Shaw-Fay p-values on the ITT only where missing death or discharge dates are imputed in the placebo group as censored at the time of last follow up and in the experimental group are imputed as events at day 28.
  - Figure with Kaplan-Meier curves and Shaw-Fay p-values on the ITT only where missing death or discharge dates are imputed in both groups as events at day 28.
  - For any imbalance seen in baseline characteristics ( $p < .05$ ) perform a cox proportional hazards model with deaths receiving event times of 28 days. Missing discharge dates will be censored at last follow up time.

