    - P-value obtained using Shaw-Fay method (here only treat deaths as worst rank and missing as censored)
  - Table duration of oxygenation: defined as time of oxygen first administered, to time off oxygen (in hours) noting min, 25%tile, 50%tile, 75%tile, max [14.2.5.3.x]
    - Table is restricted to those requiring oxygen at any point during the study.
    - P-value obtained using Shaw-Fay method (here only treat deaths as worst rank and missing as censored)
  - Figure using Kaplan-Meier plot
    - Figure includes all subjects – where subjects not requiring oxygen have 0 hours.
    - Figure is repeated, but restricted to those requiring oxygen at any point during the study.
- Admission to ICU
  - Table N (%) of requiring ICU (Y/N) at any point during the study, and at each time point [14.2.6.1.x]
    - P-value obtained using test of proportions
  - Figure of proportions at each time point
  - Table duration of ICU: defined as time subject admitted to ICU, to time discharged from ICU (in hours) noting min, 25%tile, 50%tile, 75%tile, max [14.2.6.2.x]
    - Table includes all subjects – where subjects not requiring ICU have 0 hours.
    - P-value obtained using Shaw-Fay method (here only treat deaths as worst rank and missing as censored)
  - Table duration of ICU: defined as time subject admitted to ICU, to time discharged from ICU (in hours) noting min, 25%tile, 50%tile, 75%tile, max [14.2.6.3.x]
    - Table is restricted to those requiring ICU at any point during the study.
    - P-value obtained using Shaw-Fay method (here only treat deaths as worst rank and missing as censored)
  - Figure using Kaplan-Meier plot
    - Figure includes all subjects – where subjects not requiring ICU have 0 hours.
    - Figure is repeated, but restricted to those requiring ICU at any point during the study
- Intubation/mechanical ventilation
  - Table N (%) of requiring mechanical ventilation (Y/N) at any point during the study, and at each time point [14.2.7.1]

- P-value obtained using test of proportions
- Figure of proportions at each time point
- Table duration of mechanical ventilation: defined as time subject placed on mechanical ventilation, to time extubated (removed from mechanical ventilation) noting min, 25%tile, 50%tile, 75%tile, max [14.2.7.2.x]
  - Table includes all subjects – where subjects not requiring mechanical ventilation have 0 hours.
  - P-value obtained using Shaw-Fay method (here only treat deaths as worst rank and missing as censored)

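### Two oxygen-duration rules in SAP section 12 give wrong values if followed literally: midnight stop times have no floor, and patients lost on oxygen are carried to Day 28

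*SAP*

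**What the plan says.** SAP section 12 (supplemental oxygen) measures duration in hours from first administration to the time off oxygen. Four rules bear on the value each patient receives:

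- Missing stop time: "A time of 00:00 will be imputed for subjects with a stop date but missing stop time".
- No stop date: "Subjects without stop date will be censored at 28 days".
- End of the course: "Resolution is defined as off oxygen".
- All-subjects table and figure: patients who never used oxygen are included, "where subjects not requiring oxygen have 0 hours".

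The Shaw-Fay test is then applied twice, to all subjects (table 14.2.5.2) and to oxygen users only (table 14.2.5.3). Each time the note is "here only treat deaths as worst rank and missing as censored". Kaplan-Meier figures are drawn for both sets.

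Elsewhere the plan censors incomplete follow-up when observation ends. SAP section 7 censors time to death at last contact for patients lost before 28 days. SAP section 11 says its primary-endpoint table and figures "should censor patients with missing discharge date at the time of last follow up". Protocol section 9.1 says "Patients who withdraw consent will be counted as being censored at the time of withdrawal".

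**The concern.** Both rules assign values that the data cannot support.

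Midnight is the earliest moment of the stop date. If oxygen also started on that date, the imputed stop precedes the start and the duration is negative. In a rank test, that patient does better than everyone who never needed oxygen. A Kaplan-Meier plot has no place for a negative time, and the tables report a minimum.

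The Day 28 rule suits a patient followed to Day 28 and still on oxygen. Applied to a patient lost on Day 3, it keeps that patient in the risk set as a known oxygen user for weeks in which nothing was observed. By analogy with the ranking in SAP Appendix 1, such a patient falls near the worst end of the survivors.

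A secondary point concerns the definition of resolution. The endpoint heading and the matching objective also cover an increase above the baseline oxygen requirement, but resolution requires being off oxygen. Chronic oxygen use is recorded at screening (Protocol 6.2.1.3), is tabulated at baseline (SAP section 3) and is not an exclusion (Protocol 4.4). A chronic user who returns to usual use has no stop date and is carried unresolved to Day 28.

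At stake are two tables, two p-values and two Kaplan-Meier figures for a named secondary objective.

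**Working it through.** The plan states no figure for oxygen duration, so there is none to reproduce. The check follows each rule through.

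**Midnight rule.** Duration = imputed stop minus start.

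- Start 08:00, same-day stop, no stop time: 0 - 8 = -8 h.
- Start 14:00, same-day stop, no stop time: 0 - 14 = -14 h. The true value lies between 0 and 24 - 14 = 10 h.
- Start 23:59, same-day stop, no stop time: -23 h 59 min, the extreme.
- Start 14:00, stop next day, no stop time: 24 - 14 = 10 h. The true value lies between 10 and 34 h, so the understatement is 0 to 24 h (12 h on average if stop times are uniform over the day).

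**Day 28 rule, one patient.** Lost on oxygen at Day 3, with both times counted from the same origin: 28 - 3 = 25 unobserved days carried as on oxygen. The SAP does not say whether the 28 days run from randomization or from the start of oxygen.

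**Day 28 rule, illustration.** The documents give no oxygen durations. As an assumption, the planning distribution for hospital stay stands in: log-normal with log mean 1.83 and log SD 0.66 (sample-size table, Protocol 9.2). Everyone starts on oxygen and there are no deaths. Dropout is 5%, 10% or 15%, around the 10% allowance in Protocol 9.2. Losses are uniform over Days 0-7 or Days 0-28. With 400,000 simulated patients, the Kaplan-Meier results for censoring at last follow-up versus Day 28 are:

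| Dropout, days of loss | Lost while on oxygen | Median (days) | 75th percentile (days) | On oxygen just before Day 28 |
|---|---|---|---|---|
| 5%, 0-7 | 3.9% | 6.23 vs 6.38 | 9.7 vs 10.3 | 1.1% vs 5.0% |
| 5%, 0-28 | 1.4% | 6.24 vs 6.28 | 9.7 vs 9.9 | 1.2% vs 2.5% |
| 10%, 0-7 | 7.8% | 6.23 vs 6.56 | 9.7 vs 11.1 | 1.2% vs 8.8% |
| 10%, 0-28 | 2.8% | 6.25 vs 6.32 | 9.8 vs 10.1 | 1.1% vs 3.8% |
| 15%, 0-7 | 11.6% | 6.22 vs 6.76 | 9.8 vs 12.1 | 1.1% vs 12.6% |
| 15%, 0-28 | 4.1% | 6.24 vs 6.35 | 9.7 vs 10.2 | 1.1% vs 5.0% |

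Censoring at last follow-up reproduces the curve without dropout. Hand check of the third row: patients lost on oxygen (7.8%) plus non-dropouts still on oxygen (0.90 x 1.1% = 1.0%) gives 8.8%.

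**Chronic users.** The documents give no share. If 2%, 5% or 10% of patients are never recorded as off oxygen, the proportion on oxygen just before Day 28 is 3.1%, 6.1% or 11.0%, against about 1% with none. For 5%: 5% + 0.95 x 1.1% = 6.0%, which agrees up to rounding. The 75th percentile becomes about 10.1, 10.6 or 11.8 days.

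**The case against.** The best defence is that the consequence is small. Both rules apply equally to both arms of a blinded trial. If missing stop times and early losses are unrelated to treatment, the permutation test stays valid under the null and the rules mainly add noise. This is one of many secondary endpoints, and Protocol 9.2 does not promise power for them. The Day 28 sentence was probably written for patients still on oxygen at the end of follow-up. All of that stands. It does not rescue the descriptive percentiles and curves, which are distorted even with balanced arms. Nor does it help if loss differs by arm. The sentence as written covers everyone without a stop date.

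Four stronger readings are tempting, and the documents do not support them:

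- *The Day 28 rule contradicts the Shaw-Fay note on missing data.* That note gives no censoring time, so the two are compatible. The inconsistency is with SAP sections 7 and 11 and Protocol 9.1.
- *The whole dropout allowance (10% of 290 = 29 patients) is affected.* Only patients lost while on oxygen and without a stop date are. Even with all 290 on oxygen for stay-length courses, 10% dropout gives 2.8% to 7.8%, or about 8 to 23 patients. Anyone weaned before being lost would ordinarily have a stop date from the discharge chart review (Protocol 6.2.8).
- *All oxygen courses are shortened.* Only those with a stop date and no stop time are. A negative value also needs a same-day start, and ranking ahead of never-users arises only in the all-subjects analysis.
- *Chronic users can never resolve.* A chronic user could come off oxygen altogether, and the endpoint heading allows a reading of off oxygen above baseline. The defect is that two wordings have not been reconciled.

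**Conclusion.** The point holds as a defect in two stated rules. The midnight rule gives impossible values for same-day courses without a stop time (down to almost -24 h) and understates later-ending ones by up to 24 h. The Day 28 rule treats patients lost on oxygen as observed users to the end of the study, unlike the plan's censoring for mortality and the primary endpoint. Under the assumed inputs, the Day 28 rule moves the 75th percentile from about 9.7 days to between 9.9 and 12.1 days. It raises the share on oxygen just before Day 28 from about 1% to between 2.5% and 12.6%. These figures rest on hospital stay as a proxy for oxygen duration and on assumed dropout timing. In the all-subjects analysis, never-users would change them. The mismatch over baseline oxygen need is real but secondary. The numbers of missing stop times, losses on oxygen and chronic users are not in the documents, so the actual effect cannot be sized. The primary analysis, the sample size and the test of any oxygen use are unaffected.

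**What to change.** Change two SAP sentences before unblinding:

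1. Bound a missing stop time below by the start time, for example by taking the midpoint of the possible interval on the stop date. A 14:00 same-day course becomes (24 - 14) / 2 = 5 h. A later stop date is set to 12:00, with an error of at most 12 h. The floor is essential; the midpoint is one reasonable choice.
2. Censor patients without a stop date at last contact, or at Day 28 only if followed to Day 28, and state the origin of the 28 days.

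Both use data already collected, since SAP sections 4, 7 and 11 rely on the date of last contact.

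Then reconcile the definition of resolution with the endpoint's reference to baseline need. The documents show chronic oxygen use and a yes/no oxygen requirement, but no baseline level. Resolution as a return to baseline may therefore not be derivable. If no level is captured, a sensitivity analysis excluding chronic users would serve. The cost is a few lines of SAP text and programming, with no new data collection.
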